Recent advances in continuous glucose monitoring (CGM) technology including greater accuracy, longer wear time, and no need for calibration, have led to an increase in use.¹² Randomized controlled trials of modern devices demonstrate improvement in A1c, time target range, hypoglycemia and patient reported outcomes in persons with type 2 diabetes (T2D).^{13,14,15} Moreover, real-world evidence demonstrates a reduction in A1c, diabetes distress, and hypoglycemia, and high ease of use.¹⁶ Other real world evidence found an association between near-continuous CGM and reduced hospitalizations and acute diabetes complications.^{17,18} Among older adults, treatment satisfaction and use was high, and associated with improvement in glucose control.^{19,20} However CGM is underutilized for most patients with T2D due to a variety of factors, including costs and coverage issues, time constraints imposed by implementation and use, and complexity of obtaining and interpreting data.^{12,21} In addition, there limited studies addressing optimal strategies for implementation in busy clinics. In this study we evaluate a remote CGM program utilizing Dexcom G6 CGM for recently hospitalized patients with T2D.

Aim 1: Determine the efficacy of CGM following hospital discharge among patients with T2D. We will record change in glucose metrics from discharge to 12 weeks follow-up, including % time in range 70-180 mg/dl (TIR), % time below 70 mg/dl, 54 mg/dl, and above 180 mg/dl (TAR), severe (level 3) hypoglycemic events, mean glucose, coefficient of variation, and A1c. **We will assess the primary objective by testing the relationship between CGM use (including prior inpatient use) and either change in glucose metrics or individualized % of TIR.**

Aim 2: Evaluate the utility of CGM use and impact of remote monitoring dashboard among recently hospitalized patients with T2D. A dashboard will identify patients not meeting personalized % TIR, triggering customized reports and decision support to be communicated to the patient and the usual diabetes provider. We will assess the proportion of patients with successfully transmitted data as well as change in insulin dose. A survey to the usual diabetes provider will assess usability of reports and decision support.

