| Diabetes history | x | | | | | | | |
| Hospitalization history | x | | | | | | | |
| MSPSS scale | x | | | | | | | |
| eHEALS score | x | | | | | | | |
| SNS3 | x | | | | | | | |
| DTSQ (original plus change at screen and week 12) | | | | | x | | | |
| DDS | x | | | | x | | | |
| BenCGM, BurCGM | | | | | x | | | |
| Additional patient questions | | x | x | x | x | | | x |
| Patient barriers | | | | | | | | x |
| Ascertain health care utilization | x | x | x | x | x | x | x | x |
| Record CGM data | | x | x | x | x | | | x |
| Adverse events | | x | x | x | x | x | x | x |
| Insulin/DM medication use | x | x | x | x | x | x | x | x |
| A1c | x | | | | x | | | x |
| Usual Provider Survey | | | | | x | | | |

CMN=certificate of medical necessity, MSPSS=Multidimensional Scale of Perceived Social Support, eHEALS=eHealth Literacy Scale Diabetes, DTSQ=Diabetes Treatment Satisfaction Questionnaire, BenCGM=Benefit of CGM score, BurCGM=Burdens of CGM score,

DDS=Diabetes Distress Scale, SNS3=Subjective Numeracy Scale-3. In-Person clinic visits will be conducted at either Outpatient Care East or McCampbell Hall. Telephone visits may be converted to in-person visits as needed.

Initial Assessment: Trained interviewers will perform initial data collection.

- Contact information, including email address, best times to reach the patient, contact information for 2 additional individuals, and primary care provider (PCP).
- Demographics, medical, social history
- Multidimensional Scale of Perceived Social Support (MSPSS): Social support is an environmental factor that is associated with readmissions⁴⁹, determines behavior in SCT and influences self-efficacy⁵⁰ and will be measured using the MPSS.⁵¹
- Electronic health literacy: Baseline perceived eHealth literacy will be measured by the eHealth Literacy Scale (eHEALS), in which a score of 28 was used as the cut-off for high or low ehealth literacy.⁵² The scale is comprised of 8 items on a 5-point Likert scale from 1 (strongly disagree) to 5 (strongly agree).
- Subjective Numeracy Scale-3 (SNS-3): The SNS-3 is a validated 3-item version of the longer SNS that was found to be reliable and valid to be used as a measure of subjective numeracy.⁵³

- Comorbidity is key determinant of readmission; it is measured with the Charlson comorbidity index.⁵⁴

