The database used for this study is REDCap, which is a secure web-based application for building and managing data. It is designed specifically for clinical research and administered by the OSU Center for Clinical and Translational Research. Permission for data access or entry will be granted or revoked at a level that is appropriate for each individual involved in the study. Following verification, data will be locked. Data and data labels can be downloaded selectively (for interim progress reports) or in entirety (end of study) directly from REDCap in SAS or Excel format.

Baseline Data:

- Demographics: gender, race/ethnicity, age, marital status, education, employment, insurance, marital status, contact information
- History: diabetes duration, tobacco use, microvascular/macrovascular complications, heart failure, conditions requiring anticoagulation (thromboembolism, atrial fibrillation), hypertension, hyperlipidemia, liver disease, hypoglycemia awareness, reason for hospital admission
- Medications: pre-admission, discharge, and follow-up insulin use and total daily dose, insulin type, other glucose-lowering medications, steroid use, anticoagulants, antiplatelets
- Exam: weight, height, BMI
- Surveys: MPSSS, eHEALS, SNS-3
- Labwork: eGFR, A1c, glucose level on admission and discharge
- Patient reported outcomes: DTSQs, DDS
- Additional patient questions about CGM use
- CGM target (Table 4)

Visit 1, 2, 3:

- Glucose data: detailed below
- Communication: to usual care provider (summary only, summary with advice)
- Diabetes medications, bolus insulin use, basal insulin dose, missed doses
- Adverse events (sensor irritation, infection, bleeding)
- Additional patient questions about CGM use
- Healthcare Utilization: PCP visit, education visit, endocrinology visit, hospital readmission, emergency visit
- CGM target (Table 4)

Visit 4:

- Glucose data: detailed below
- Communication: to usual care provider (summary only, summary with advice)
- Diabetes medications: non-insulin medication use by class, bolus insulin use, basal insulin dose, missed doses
- Adverse events (sensor irritation, infection, bleeding)
- Healthcare Utilization: PCP visit, education visit, endocrinology visit, hospital readmission, emergency visit
- Patient reported outcomes: DTSQs, DTSQc, DDS, BenCGM, BurCGM
- Additional patient questions about CGM use
- A1c
- CGM target (Table 4)

Visit 5, 6

- Glucose data: detailed below

Visit 7

- Glucose data: detailed below

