- Diabetes medications: non-insulin medication use by class, bolus insulin use, basal insulin dose, missed doses
- Adverse events (sensor irritation, infection, bleeding)
- Healthcare Utilization: PCP visit, education visit, endocrinology visit, hospital readmission, emergency visit
- A1c
- Additional patient questions about CGM use, barriers to use

Glucose data: A minimum of 14 consecutive days with 70-80% of data overall is recommended for analysis.⁶²

- Coefficient of variation (CV) is calculated as the standard deviation/mean glucose and is the preferred measure of glucose variability.
- % Time in target range (TIR) 70-180 mg/dl
- Hyperglycemia
 - Time spent >180 mg/dl (TAR)
 - Time spent >300 mg/dl
- Hypoglycemia
 - Time spent <54 mg/dl
 - Time spent <70 mg/dl (TBR)
- Additional Measures
 - Mean sensor glucose
 - % time of CGM data
 - Sensor Failures

Usual care providers: usual care providers will complete a 12 item questionnaire which will include

- provider type
- years in practice

- practice setting
- specialty
- % of patients with diabetes (5-level category)
- familiarity with CGM (5-point Likert)
- frequency of CGM interpretation (4 level category)
- 5-item Likert scale:
 - SUS-2 (ease of use, cumbersome to use)
 - CGM report helpful in assessing glucose control
 - ambulatory glucose profile helpful for making adjustment in therapy
 - report recommendations helpful for making adjustments to therapy
- Whether Clarity website was accessed

Endpoints:

Aim 1:

Primary

- Change % TIR 70-180 mg/dl from baseline (week 2) to 12 weeks

Secondary

- Change in % of patients meeting individualized TIR (Table 3)
- Change % TAR, TBR, % time <54 mg/dl, mean glucose, CV from baseline to 12 weeks
- Change in A1c from baseline to 12 weeks

Aim 2:

Primary

- % CGM wear time at 12 weeks

Secondary

- % of patients with % wear time >70% at 12 weeks.
- Reason for CGM wear <70% (loss to follow-up, issue with mobile phone, sensor/transmitter loss or damage, adverse sensor event, patient preference [state reason], other)
- % with transmitted data at 12 weeks
- % with dashboard driven summary, dashboard driven advice sent to usual care provider by 12 weeks
- Change in basal insulin dose from discharge to 12 weeks

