- Usual Care Provider usability: SUS-2 (ease of use, cumbersome to use), CGM report helpful in assessing glucose control, ambulatory glucose profile helpful for making adjustment in therapy, report recommendations helpful for making adjustments to therapy, whether Clarity website was accessed.
- % of usual care providers reporting review of data

Aim 3:

Primary:

- Change in DTSQ scores from baseline to 12 weeks

Secondary:

- Change in DDS from baseline to 12 weeks
- Patient reported outcomes (DTSQ, DDS, BenCGM, BurCGM).

Endpoints for Exploratory Aim 1:

- healthcare utilization (clinic visits, education visit, hospital readmission, emergency visit)

Endpoints for Exploratory Aim 2 (Extension Phase): *By 18 months (the end of the last 90 day visit), we anticipate that a subset of patients (75%) will have at least 12 additional weeks of data following the primary endpoint at 12 weeks. We will assess the following metrics among users and compare to nonusers:*

- Change in % CGM wear from 12 weeks to 24 weeks
- Change in glucose metrics from 12 weeks to 24 weeks.
- Change in insulin dose from 12 weeks to 24 weeks.
- Patient reported barriers to continued CGM use (5-point Likert from not important at all to very important, unless otherwise noted):
 - Cost/coverage concerns (if important or very important, then answer the following)

- Insurance did not cover CGM (yes/no)
- Insurance partially covered CGM but co-pay was too high (yes/no)
- Usual care provider would not prescribe CGM (yes/no)
- Too much hassle to order/obtain CGM
- Too many alarms
- Having device attached to the body/lack of privacy
- Do not understand what to do with the information
- Unreliable/does not work
- Discomfort/pain
- Too time-consuming
- Interferes with sleep
- Healthcare utilization (PCP visit, education visit, endocrinology visit, hospital readmission, emergency visit)

Sample Size

We anticipate enrollment of 120 patients over a 1 year period with 20% drop-out. The following data support this sample size.

Aim 1:

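### Aim 1 promises to record severe (level 3) hypoglycemic events, but they are its only metric with no named Aim 1 endpoint, no itemised data field and no event-specific analysis

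*Combined protocol and SAP*

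**What the plan says.** In Specific Aims, Aim 1 opens with "We will record change in glucose metrics from discharge to 12 weeks follow-up". It then names time in range, time below 70 and below 54 mg/dl and time above 180 mg/dl, and ends with "severe (level 3) hypoglycemic events, mean glucose, coefficient of variation, and A1c". That makes eight metrics.

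Under Endpoints, Aim 1, the primary is "Change % TIR 70-180 mg/dl from baseline (week 2) to 12 weeks". The secondary list has the proportion of patients meeting their individualized time-in-range target, A1c, and "Change % TAR, TBR, % time <54 mg/dl, mean glucose, CV from baseline to 12 weeks".

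Table 5 has an open row covering visits 1 to 7: "Adverse events | | x | x | x | x | x | x | x". The visit lists under Data Collection and Management, and again under Sources of Materials (A.1.b), fill that row in as "Adverse events (sensor irritation, infection, bleeding". The hypoglycemia items in both lists are sensor time below 54 and below 70 mg/dl.

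The endpoint for Exploratory Aim 1 is "healthcare utilization (clinic visits, education visit, hospital readmission, emergency visit". No cause of visit is listed.

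**The concern.** A severe low is the most serious hypoglycemic outcome that the plan names, and the one that sensor summaries cannot stand in for. The study also takes part in insulin dosing: under Communication with Usual Care Providers, the team advises patients who miss their targets on titrating basal insulin. Potential Risks accepts that sensor error could in theory lead to overtreatment. The Work Plan commits the first manuscript to safety as well as efficacy.

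If the plan is followed as listed, that manuscript would have no defined count of these events. An analyst can add a summary of sensor data at any time, because the data will exist. An event that was never asked about at a visit can be recovered only in part from other records.

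**Working it through.** The plan states no figure for level 3 hypoglycemia, so there is none to reproduce. The check has three steps.

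**Step 1: match Aim 1 to the rest of the plan.**

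| Aim 1 metric | Named Aim 1 endpoint | Itemised data field |
|---|---|---|
| Time in range | yes (primary) | yes |
| Time above 180 mg/dl | yes | yes |
| Time below 70 mg/dl | yes | yes |
| Time below 54 mg/dl | yes | yes |
| Mean glucose | yes | yes |
| Coefficient of variation | yes | yes |
| A1c | yes | yes |
| Level 3 events | no | no |

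Seven of eight are carried through. The adverse-event item appears six times: three times under Data Collection and Management (visits 1-3, visit 4, visit 7) and three times under Sources of Materials for the same visits. It has the same three examples each time, and none is hypoglycemia. Level 3 is not defined, and the Analysis section does not name it.

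**Step 2: can the sensor endpoints supply the count?** No. A 14-day window has 14 × 24 × 60 = 20,160 minutes, and 1% of that is about 202 minutes. That could be one long episode or ten of about 20 minutes each, and it does not show whether the patient needed help.

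**Step 3: what would a count show?** Inputs: 120 patients enrolled and 20% dropout (Sample Size), so 120 × 0.8 = 96 completers, and the 80 used in the power statements. The 12-week patient risk r is my assumption.

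- Zero events, two-sided exact 95% upper limit = 1 − 0.025^(1/n).
- Chance of at least one affected patient = 1 − (1 − r)^n.

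| | n=80 | n=96 | n=120 |
|---|---|---|---|
| Upper limit with zero events | 4.5% | 3.8% | 3.0% |
| Chance of any, r = 0.5% | 33% | 38% | 45% |
| Chance of any, r = 1% | 55% | 62% | 70% |
| Chance of any, r = 2% | 80% | 86% | 91% |
| Chance of any, r = 5% | 98% | 99% | over 99% |

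Exact 95% (Clopper-Pearson) intervals at n=120: 1 patient is 0.8% (0.02 to 4.6%), 2 patients 1.7% (0.2 to 5.9%), 3 patients 2.5% (0.5 to 7.1%).

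**The case against.** The strongest reply is that the plan is not silent, and much of that reply is right.

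- **Analysis.** Aim 1 counts level 3 events among its glucose metrics. The Analysis section regresses change in glucose metrics on wear time and reports binary variables as number and percentage. Exploratory Aim 2 looks at change in glucose metrics from week 12 to week 24. So these rules cover the events in name. They still do not give a count from discharge to week 12, and a linear model of change does not suit a rare event with no baseline value.
- **Capture.** The Table 5 row is open, and the three listed adverse events may be examples. Protections against risk sends severe adverse events to the principal investigator and the review board, and that clause is not limited to study-related events. Retention provides for monitoring of the institution's records and queries to the primary care physician up to 12 weeks. Emergency visits and readmissions are recorded. The satisfaction questionnaire asks about perceived frequency of lows.

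A reader might therefore infer the opposite extreme, that severe lows will go unrecorded. The documents do not support that. The REDCap forms are not in them, and several routes could pick up an event. What is missing is a definition, a standard question and a named result.

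A reader might also infer that the change in time below range is the plan's safety result and is invalid because its baseline falls after CGM has begun. That goes too far. The plan lists the change under efficacy and never calls it the safety result. The on-CGM baseline is shared by every sensor change endpoint, including the primary. Sensor data are recorded at weeks 1-2, 4, 8 and 12 ("Record CGM data | | x | x | x | x | | | x"), so showing levels by visit is a choice of tabulation. The documents give no distribution of time below range for this population from which to size an effect of that baseline.

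**Conclusion.** The point holds for level 3 events. They are the one Aim 1 metric of eight without a named Aim 1 endpoint, an itemised field or an event-specific analysis, and none of the indirect routes gives a defined count. It should be fixed. It does not affect the primary endpoint.

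The size rests on assumed risks. It cannot be said that there will probably be events to count: below about 1% risk, zero is a realistic result (55 to 67% likely at 0.5%, for n from 120 down to 80). A zero obtained by asking everyone would still be informative, because it bounds the risk at 3.0 to 4.5%. A zero from an unasked question bounds nothing.

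**What to change.** 1. Define level 3 hypoglycemia in the protocol, for instance as a low for which the patient needed another person's help.
2. Add one standard question on it to the adverse-event review at visits 1-4.
3. Add to Aim 1 Secondary: number of level 3 events, and number (%) of patients with at least one, from discharge to week 12, with an exact 95% interval. The denominator is all patients discharged with a sensor, with follow-up time shown.
4. For visits already completed, use the institution's records, severe adverse event reports and primary care physician queries, and state that this capture is incomplete.

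Optional and descriptive only: show time below 70 and below 54 mg/dl as levels at weeks 1-2, 4, 8 and 12 beside the change scores. Do not present a fall from the on-CGM week 2 baseline as proof that the program reduced hypoglycemia.

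The cost is one definition, one question at contacts where adverse events are already reviewed, and one line in a results table, plus record review for past visits. No visit is added and no endpoint is removed. The downsides are wide intervals and a safety picture that may look less favourable.

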- Discharge medications: The complexity of the discharge regimen will be assessed as number of injections per day, use of basal, prandial, and premix insulin, total units of insulin per day, basal dose, and other diabetes medications by treatment class.

Intervention:

Device use: Participants will wear the Dexcom G6 CGM throughout the study. All patients will receive education from trained personnel in its use according to manufacturer instructions. Target ranges will be set up as 70-180 mg/dl. Patient alerts will be customized, but generally <70 mg/dl for hypoglycemia and >200 mg/dl (surgical patients) or 300 mg/dl (nonsurgical patients).

Device Connections, Alerts, and Dashboard: Data will be obtained using the Clarity app which will be set up on the patient smartphone. A sharecode will be set up for 1 year and documented in the patient's electronic medical record. The patient will also be linked directly to the study Clarity account. Subjects not meeting % time in range metrics over the previous 14 days will be identified (Table 4).

Table 4. Target Metrics

| Population* | % TAR | % TIR | % TBR |
|--|-------|-------|-------|
| Hypoglycemia risk, eGFR <30 ml/min/1.73m ² , >age 65 | 50 | 50 | 1 |
| Otherwise healthy or recent surgery (within 2 weeks or wound infection)* | 25 | 70 | 4 |

*Goal % of time in target range (70-180 mg/dl) may shift categories depending on predominant clinical characteristics. TAR=time above range (>180 mg/dl), TIR-time in range (70-180 mg/dl), TBR=time below range (< 70 mg/dl)

Discharge: Patients will also receive basic survival skills education (regarding glucose targets, consistent carbohydrate meals, basal insulin titration). The discharge regimen and all prescriptions and clinical follow-up will be determined by the primary team with input from the diabetes consult service if requested. All patients will receive standard discharge instructions using the EMR as per usual practice. Hospital discharge is coordinated by the primary team and patient care resource manager who arranges follow-up prior to discharge. A discharge summary is sent to the primary provider per routine practice.

Communication with Usual Care Providers:

- **Enrollment** Providers (up to 2 providers per patient, primary care and endocrinologist, up to 200 providers total) will be notified of initial patient enrollment in the study using a standardized letter containing the patient's Clarity sharecode and instructions for accessing Clarity.

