- **Benefit of CGM (BenCGM) and Burdens of CGM (BurCGM).** Each questionnaire contains 8 items and was originally validated in a sample of 431 adolescents with type 1 diabetes.⁵⁹ In a large sample of 1334 adults with type 1 diabetes, CGM users perceived more benefits and less burden compared to those who were not using CGM, though older users (above age 50) had higher mean BurCGM scores, and users above age 65 reported more worry and more difficulty understanding CGM information than younger users.⁶⁰ Both questionnaires showed high internal consistency (Cronbach’s α of 0.89 for BenCGM, and 0.87 for BurCGM) and reliability. Previous measures of glucose monitoring satisfaction were lengthy, or omit major themes specific to CGM. Possible limitations include a high mean score for BenCGM, indicating possible ceiling effect limiting the ability to detect improvement over time and conversely, a low mean BurCGM score, reducing the ability to detect further worsening of the score.
- **Diabetes Distress:** The Dexcom G6 was associated with reductions in diabetes distress, a quality of life measure, in a recent observational study¹⁷ using the Diabetes Distress Scale (DDS; 17-item scale; 4 subscales; higher scores indicate greater distress).⁶¹ Answers to each item are based on a 6-point Likert scale, rated from 1 (“not a problem”) to 6 (“a very serious problem”) for the past month. Subscales evaluate emotional burden (five items), regimen distress (five items), interpersonal distress (three items), and physician distress (four items). The total mean score is calculated and a score of <2.0 is considered as “little or no distress,” 2.0-2.9 as “moderate distress,” and ≥ 3.0 as “high distress.” This copyrighted scale is available free of charge to non-profit institutions for use in clinical care and research. In contrast, the Problem Areas in Diabetes (PAID), was not significantly affected in a recent study.¹⁷
- **Additional Questions:** In addition we will ask the patient whether they have made a change to their basal insulin, diet, or activity in the past 7 days in response to CGM data (Yes/No) and whether the usual care provider reviewed CGM data. At the end of the extension phase, we will ask the patient about important barriers to ongoing use (1-5 Likert scale).

Data Collection and Management:

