- DTSQ: In the LANDMARK study, 94% of participants with T2D were satisfied or very satisfied (Question 1 of the DTSQ). In a randomized study of 101 patients with T2D using the Freestyle Libre Flash glucose monitor (an intermittently scanned glucose monitoring device), mean (SD) DTSQc score per subject for each question was 2.47 (0.77) with CGM vs. 2.18 (0.83) in the control group ($P = 0.053$). Thus, we would anticipate a change in DTSQc that is proportional.¹³
- DDS: In the LANDMARK study, the DDS decreased from 2.67 (SD 0.65) to 1.85 (0.65) from baseline to 12 weeks. We would anticipate a similar change in DDS score.
- BenCGM, BurCGM: In a large study of patients with type 1 diabetes, there was a significant difference in BenCGM (4.48 vs. 4.19, $p<0.001$) and BurCGM (1.69 vs. 2.35, $p<0.001$) among CGM users vs. non-

users, respectively. Thus, we anticipate that both scores will be associated with CGM wear time in the present study.

Analysis

Descriptive statistics will summarize the sample characteristics and distribution of each variable. Data will be screened for normality, outliers, and homogeneity. Continuous variables with normal distribution will be reported as mean (standard deviation) while non-normal distribution will be reported as median (interquartile range). Binary variables will be reported as number (percentage). Change over time in continuous variables will be reported as paired t-test or nonparametric test as appropriate. Difference of proportions between groups for binary variables is tested by Fisher's test (two groups) or chi-square test (three or more groups). Statistical significance will be determined at p-value of <0.05.

For Aim 1, linear regression can be used for checking the relationship between %CGM wear time and change in glucose metrics. Appropriate transformation may be needed if the residual plots show obvious violation of linear regression assumptions. Logistic regression can be used for checking the association between % CGM wear time and % meeting individualized TIR or change in % of patients who meet their individualized TIR. For choosing the predictors of change in TIR from baseline to 12 weeks, we can first include a subset of the exploratory variables depending on the descriptive statistics and clinical context. If necessary, further variable selection (stepwise selection) can be conducted to make the analysis reliable. In addition, we will assess baseline predictors of glucose metrics.

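### The Aim 1 logistic model of meeting individualized TIR on CGM wear time specifies no adjustment for the Table 4 goal row, although that row sets the pass mark

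*Combined protocol and SAP*

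**What the plan says.** The Analysis section, under Aim 1, proposes: "Logistic regression can be used for checking the association between % CGM wear time and % meeting individualized TIR". No covariate or stratum is named for this model. The variable selection described next in that paragraph is for predictors of change in TIR, a different outcome. The paragraph closes with a general intention to look at baseline predictors of glucose metrics.

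Table 4 (Target Metrics) defines what meeting the goal means. Its columns are TAR, TIR and TBR:

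- First row: "eGFR <30 ml/min/1.73m ² , >age 65 | 50 | 50 | 1". The TIR goal is 50%.
- Second row: "Otherwise healthy or recent surgery (within 2 weeks or wound infection)* | 25 | 70 | 4". The TIR goal is 70%.

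The footnote adds that the goal "may shift categories depending on predominant clinical characteristics". The Baseline Data list and the lists for Visits 1 to 4 record each patient's CGM target, but the Analysis section does not use it.

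Specific Aims describes the primary objective as "testing the relationship between CGM use (including prior inpatient use) and either change in glucose metrics or individualized % of TIR". The Endpoints section makes change in % TIR primary and lists individualized TIR as secondary. It cites Table 3 for the targets, but they are in Table 4.

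**The concern.** A covariate usually might predict an outcome. Here the goal row is part of the outcome's definition: a patient with 60% TIR passes in one row and fails in the other. The row is also set by patient characteristics (age, kidney function, hypoglycemia risk) that could plausibly go with how much the device is worn. If they do, a model without the row mixes two things: whether wear goes with better glucose, and whether patients who wear the device more, or less, were given the lower TIR mark.

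The problem arises even when rows stay fixed and the outcome is simply met or not met. The error can run either way. More wear in the 50% row would produce a spurious benefit; less wear there would mask a real one or suggest harm. What is at stake is one of the two relationships that Specific Aims names for the primary objective, on an endpoint that the Endpoints section ranks as secondary.

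**Working it through.** **The plan's own figure.** The Sample Size section gives 99% power for TIR with n = 80, difference 15, SD 15 and significance level 0.05. For a one-sample t-test the noncentrality is (15/15) × √80 = 8.94, and power exceeds 99.99%, consistent with the stated figure. It concerns a mean. The plan gives no power for the logistic model.

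**Pass rates at identical glucose.** Take TIR as normal with the plan's mean 60 and SD 15.

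- 50% goal: 1 − Φ((50 − 60)/15) = 0.748
- 70% goal: 1 − Φ((70 − 60)/15) = 0.252
- Odds ratio: (0.748/0.252)/(0.252/0.748) ≈ 8.8

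At mean 65.1 (the 12-week figure of a cited trial) the rates are 84% and 37%.

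**Share of patients in the 50% row.** The plan does not state it. Two routes give a range.

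- *Preliminary data, Table 1.* Age is mean 51.7, SD 10.2, so P(age > 65) = 1 − Φ(13.3/10.2) = 0.096 on a normal approximation. eGFR below 30 is 10/158 = 0.063, using the two arms' counts of 4 and 6, since the printed overall count does not fit its percentage. If the two are independent, 1 − (1 − 0.096)(1 − 0.063) = 0.153, before hypoglycemia risk is added.
- *Sample Size section.* It cites 47% meeting a 70% goal and anticipates 60% meeting individualized goals. With SD 15, 47% at the 70% goal implies mean 68.9, and then 89.6% meet a 50% goal. Solving 0.47(1 − s) + 0.896s = 0.60 gives s = 0.13/0.426 ≈ 0.305, about 31%.

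**Effect on the wear coefficient.** These simulations contain no true link between wear and TIR. TIR is as above. Wear SD is 15 points (from the cited trial in the Sample Size section), mean wear is assumed to be 80%, and n = 120 × 0.8 = 96. The wear gap is the 50% row minus the 70% row and is an assumption throughout. Rejection rates come from 1,500 trials per setting at p < 0.05; odds ratios are per 10 points of wear, from a sample of 200,000.

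| Share in 50% row | Wear gap (points) | TIR in 50% row | OR, wear only | False positives, wear only | False positives, row added |
|---|---|---|---|---|---|
| 15% | +5 | equal | 1.07 | 5.6% | 3.9% |
| 15% | +10 | equal | 1.13 | 11.1% | 4.8% |
| 15% | −10 | equal | 0.87 | 13.6% | 4.1% |
| 15% | +10 | 10 lower | 1.07 | 7.4% | 6.3% |
| 15% | +10 | 20 lower | 1.00 | 5.0% | 4.5% |
| 30% | +5 | equal | 1.10 | 9.3% | 4.6% |
| 30% | +10 | equal | 1.21 | 24.2% | 4.9% |
| 30% | −10 | equal | 0.83 | 25.1% | 5.7% |
| 30% | +10 | 10 lower | 1.11 | 9.7% | 5.0% |
| 30% | +10 | 20 lower | 1.00 | 4.4% | 4.7% |

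Extending this to n = 80 to 96, gaps of 5 to 11 points and shares of 15 to 31% gives about 6 to 34% with equal TIR, and about 4 to 15% with TIR 10 points lower in the 50% row. The top of each range also depends on the assumed spread of wear and on how its ceiling at 100% is handled. Adding the row keeps the rate near 5% (3 to 7%).

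**The case against.** **Nothing in the documents shows that wear differs by row.** This is the strongest objection, and it stands. A reader might infer a difference from two places. Specific Aims says: "Among older adults, treatment satisfaction and use was high". It makes no comparison with younger patients. The BenCGM/BurCGM section says "users above age 65 reported more worry and more difficulty understanding CGM information than younger users", but that concerns perceived burden in adults with type 1 diabetes, not wear time. Neither mentions kidney function or hypoglycemia risk. So the stronger reading, that any wear difference by age or kidney function will appear as an effect of CGM use, is not supported.

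**Equal TIR in both rows may be unrealistic.** Under Communication with Usual Care Providers, titration advice goes to patients not meeting targets, so those in the 50% row stop triggering it at a lower TIR. A lower TIR in that row is plausible, though not documented. It would shrink the bias, and at 20 points lower would cancel it.

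**The model is not stated to be univariable.** A reader might take it to contain only wear time. The plan says logistic regression can be used, so adjustment is not excluded. What can be said is that none is specified for this outcome.

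**The primary endpoint is untouched.** Change in % TIR does not use the row-specific cut-off. This limits the importance of the point.

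None of these objections removes the gap. The row still sets the pass mark, and the plan does not say that the model will account for it.

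**Conclusion.** The concern holds in conditional form. It is certain from Table 4 that the same glucose can pass in one row and fail in the other, and at the plan's mean and SD the contrast is 75% against 25%. It is also clear that the Analysis section specifies no adjustment for this. Whether the wear association is distorted depends on a wear gap between rows that the documents do not establish.

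The size therefore rests on assumptions. With 15% of patients in the 50% row and a 5-point gap, the error rate is close to nominal. With about 30% in that row, a gap of 10 to 11 points and equal TIR, it reaches roughly a quarter to a third. If TIR is 10 points lower in that row it stays at or below about 15%. The direction is unknown.

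The 50% row is easier only for TIR, which is what this endpoint uses; its time-below-range goal is stricter (1 against 4). Nothing here questions the Table 4 targets as clinical goals. This is an inexpensive improvement to a secondary analysis, not a flaw in the primary endpoint.

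**What to change.** State in the Analysis section that the logistic model of meeting individualized TIR on % CGM wear time includes, as a prespecified covariate or stratum, the Table 4 target row recorded at baseline. Naming the baseline visit matters because the row can shift and is recorded again at Visits 1 to 4. The plan should also say which visit's row scores the week-12 outcome; if it is not the baseline row, the covariate corrects only partly for patients who changed row.

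Give row-specific results descriptively only. At a 15% share the 50% row holds 0.15 × 80 = 12 to 0.15 × 96 ≈ 14 patients. With 25% failing, that is three or four failures, too few for a separate logistic fit.

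Week-2 TIR is not needed for this problem. It is measured after wear has begun and could absorb part of a real wear effect.

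The cost is a sentence or two of SAP text and one degree of freedom. No new data, visits or patients are needed, and no clinical target changes. The Table 3 citations for the targets should be corrected to Table 4 at the same time.
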